- Patients who have been treated with chemotherapy, with biological therapy or other investigational agent must have discontinued the treatment at least 2 weeks (14 days) prior to starting study drug. In case last chemotherapy contains nitrosourea or mitomycin C, the treatment must be discontinued at least 6 weeks prior to the first dose of study drug.
 - Patients, if previously treated with crizotinib must discontinue treatment at least 1 week (7 days) prior to the first dose of study drug.
- 7a. Patient must meet the following laboratory values at the screening visit:
- Absolute Neutrophil Count $\geq 1.5 \times 10^9/L$
 - Platelets $\geq 75 \times 10^9/L$
 - Hemoglobin (Hgb) ≥ 8 g/dL
 - Serum creatinine < 1.5 mg/dL and /or calculated creatinine clearance (using Cockcroft-Gault formula) ≥ 30 mL/min
 - Total bilirubin $\leq 1.5 \times$ ULN except for patients with Gilbert's syndrome who may only be included if total bilirubin $\leq 3.0 \times$ ULN or direct bilirubin $\leq 1.5 \times$ ULN
 - Aspartate transaminase (AST) $\leq 3 \times$ ULN, except for patients with liver metastasis, who are only included if AST $\leq 5 \times$ ULN
 - Alanine transaminase (ALT) $\leq 3 \times$ ULN, except for patients with liver metastasis, who are only included if ALT $\leq 5 \times$ ULN
 - Alkaline phosphatase (ALP) $\leq 5.0 \times$ ULN
 - Serum amylase $\leq 2 \times$ ULN
 - Serum lipase \leq ULN
 - Fasting plasma glucose ≤ 200 mg/dL (≤ 11.1 mmol/L)
8. Patient must have the following laboratory values within normal limits or corrected to within normal limits with supplements during screening:
- Potassium
 - Magnesium
 - Phosphorus
 - Total calcium (corrected for serum albumin)
9. Patient has life expectancy ≥ 6 weeks.
10. Patient has a WHO performance status 0-2.
11. Patient has the ability to understand and provide signed informed consent.
12. Willingness and ability to comply with scheduled visits, treatment plans, laboratory tests and other study procedures.

Patients in Arm 1 to 4 must also meet the following inclusion criteria:

13. Patients must have active brain metastases from NSCLC, confirmed by Gadolinium-enhanced MRI without concomitant leptomeningeal carcinomatosis. Dose of steroids must be stable for 5 days before the baseline brain MRI.

Note: An active brain lesion is a lesion free of any local treatment (like stereotactic radiosurgery or whole brain radiation). The following lesions are considered active:

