Grade 4 (PLT < $25 \times 10^9/L$)	Mandatory: Omit dose until resolved to \leq Grade 2, then \downarrow 1 dose level
HEPATIC	
Alkaline phosphatase and/or Gamma-glutamyl transpeptidase (GGT)	
Isolated elevations of any grade	Recommendation: Maintain dose level
Total Bilirubin** (for patients with Gilbert Syndrome these dose modifications apply to changes in direct [conjugated] bilirubin only)	
Grade 1 ($> ULN$ and $\leq 1.5 \times ULN$)	Recommendation: Maintain dose level with liver function test (LFTs)*** monitored as per protocol
Grade 2 (> 1.5 and $\leq 3.0 \times ULN$) with ALT or AST $\leq 3.0 \times ULN$	Mandatory: Omit dose until resolved to \leq Grade 1, then it is recommended: If resolved in ≤ 7 days, to maintain dose level If resolved in > 7 days, to \downarrow 1 dose level

[figure not shown]
Worst toxicity (CTCAE 4.03 Grade)*	Dose Modifications for ceritinib
Grade 3 (> 3.0 and ≤ 10.0 x ULN) with ALT or AST ≤ 3.0 x ULN	Mandatory: Omit dose until resolved to ≤ Grade 1, then it is recommended: If resolved in ≤ 7 days, to ↓ 1 dose level If resolved in > 7 days, to discontinue patient from ceritinib
Grade 4 (> 10.0 x ULN)	Mandatory: Permanently discontinue patient from ceritinib
AST or ALT	
Grade 1 (> ULN and ≤ 3.0 x ULN)	Recommendation: Maintain dose level with LFTs*** monitored per protocol
Grade 2 (> 3.0 and ≤ 5.0 x ULN) without total bilirubin elevation to > 2.0 x ULN	Recommendation: Maintain dose level with LFTs*** monitored per protocol
Grade 3 (> 5.0 and ≤ 20.0 x ULN) without total bilirubin elevation to > 2.0 x ULN	Mandatory: Omit dose until resolved to ≤ Grade 1, then ↓ 1 dose level
Grade 4 (> 20.0 x ULN) without total bilirubin elevation to > 2.0 x ULN	Mandatory: Omit dose until resolved to ≤ Grade 1, then ↓ 1 dose level
AST or ALT and concurrent Total bilirubin	
AST or ALT > 3.0 x ULN with total bilirubin > 2.0 x ULN in the absence of cholestasis or hemolysis	Mandatory: Permanently discontinue patient from ceritinib Refer to Section 6.3.4.2 for additional follow-up
RENAL	
Serum creatinine	
Grade 1 (>1 and ≤1.5 x baseline; >ULN and ≤ 1.5 x ULN)	Recommendation: Maintain dose level
Grade 2 (> 1.5 and ≤ 3 x baseline; >1.5 and ≤3.0 x ULN)	Recommendation: Omit dose until resolved to ≤ Grade 1, then it is recommended: If resolved in ≤ 7 days, then maintain dose level If resolved in > 7 days, then ↓ 1 dose level
Grade 3 (>3.0 x baseline; > 3.0 and ≤ 6.0 x ULN)	Mandatory: Omit dose until resolved to ≤ Grade 1, then ↓ 1 dose level

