6.3.4.1 Guidelines for the follow-up of laboratory hematologic abnormalities

In case of any occurrence of febrile neutropenia, neutropenia \geq grade 3 or thrombocytopenia \geq grade 3, tests must be performed weekly (or more frequently if clinically indicated) until the event resolves to \leq grade 2. Subsequent monitoring must be performed every 4 weeks. See [Table 6-4](#).

6.3.4.2 Guidelines for the follow-up of laboratory liver abnormalities and potential drug-induced liver injury (DILI) cases

In patients with any clinically relevant laboratory liver abnormality, as defined below, hepatic toxicity monitoring must include ALL of the following liver function tests (LFTs): albumin, ALT, AST, total bilirubin (fractionated if total bilirubin $>$ 2.0 x ULN), alkaline phosphatase and GGT. Note: for patients with Gilbert Syndrome, total and direct bilirubin must be monitored, but intensified monitoring applies to changes in direct bilirubin only.

[figure not shown]
In case of any occurrence of ALT/AST/total bilirubin increase to grade 2 the LFTs must be monitored weekly (or more frequently if clinically indicated) until the event resolves to \leq grade 1. Thereafter monitoring must be continued every other week (or more frequently if clinically indicated) for two additional cycles (e.g. 8 weeks). If there is no recurrence of grade 2 ALT/AST/total bilirubin elevations during this period, subsequent monitoring must be performed every 4 weeks. For patients with liver metastasis and grade 2 AST/ALT at baseline, increased monitoring is required for grade 3/4 AST/ALT; follow guidelines for grade 3 or 4 AST/ALT.

In case of any occurrence of ALT/AST/total bilirubin increase to grade 3 or 4, LFTs must be monitored weekly (or more frequently if clinically indicated) until the event resolves to \leq grade 1. Thereafter monitoring must be continued every other week (or more frequently if clinically indicated) for four additional cycles (e.g. 16 weeks). If there is no recurrence of \geq grade 2 ALT/AST/total bilirubin elevations during this period, subsequent monitoring must be performed every 4 weeks.

Patients who discontinue study treatment due to liver toxicity must be monitored weekly (or more frequently if clinically indicated) until the event resolves to \leq grade 1 or stabilization occurs (no CTCAE grade change over 4 weeks). Refer to [Table 6-4](#).

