Patients with transaminase increase combined with total bilirubin (TBIL) increase may be indicative of potential Drug Induced Liver Injury (DILI), and should be considered as clinically important events.

The threshold for potential DILI may depend on the patient's baseline AST/ALT and TBIL value; patients meeting any of the following criteria will require further follow-up as outlined below:

- For patients with normal ALT and AST and TBIL value at baseline: AST or ALT > 3.0 x ULN combined with TBIL > 2.0 x ULN
- For patients with elevated AST or ALT or TBIL value at baseline: [AST or ALT > 2 x baseline AND > 3.0 x ULN] OR [AST or ALT > 8.0 x ULN], combined with [TBIL > 2 x baseline AND > 2.0 x ULN]

Medical review needs to ensure that liver test elevations are not caused by cholestasis, defined as: ALP elevation > 2.0 x ULN with R value (ALT/ALP in x ULN) < 2 in patients without bone metastasis, or elevation of ALP liver fraction in patients with bone metastasis.

Note: (The R value is calculated by dividing the ALT by the ALP, using multiples of the ULN for both values. It denotes the relative pattern of ALT and/or ALP elevation is due to cholestatic (R <2), hepatocellular (R >5), or mixed (R >2 and <5) liver injury).

In the absence of cholestasis, these patients should be immediately discontinued from study drug treatment, and repeat LFT testing as soon as possible, preferably within 48 hours from the awareness of the abnormal results. The evaluation should include laboratory tests, detailed history, physical assessment and the possibility of liver metastasis or new liver lesions, obstructions/compressions, etc.

[figure not shown]
- Laboratory tests should include ALT, AST, albumin, creatinine kinase, total bilirubin, direct and indirect bilirubin, GGT, prothrombin time (PT)/INR and alkaline phosphatase.
- A detailed history, including relevant information, such as review of ethanol, concomitant medications, herbal remedies, supplement consumption, history of any pre-existing liver conditions or risk factors, should be collected.
- Further testing for acute hepatitis A, B, C or E infection and liver imaging (eg, biliary tract) may be warranted.
- [REDACTED]
- Additional testing for other hepatotropic viral infection (CMV, EBV or HSV), autoimmune hepatitis or liver biopsy may be considered as clinically indicated or after consultation with specialist/hepatologist.

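### Table 6-3 gives a worse liver profile a milder dose instruction: at bilirubin >1.5 to 2.0 x ULN the mandatory hold lapses when ALT and AST are both >3 to 5 x ULN

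*Protocol*

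**What the plan says.** The hepatic block of Table 6-3 (Protocol 6.3.3) has these rows:

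- **Total bilirubin Grade 2** (>1.5 to 3.0 x ULN), on condition that ALT or AST is at or below 3.0 x ULN: mandatory omission until Grade 1 or better. The same dose is then recommended if this took 7 days or less, and one level lower if longer.
- **AST or ALT Grade 2**, "Grade 2 (> 3.0 and ≤ 5.0 x ULN) without total bilirubin elevation to > 2.0 x ULN": a recommendation to maintain the dose, with liver tests monitored.
- **AST or ALT Grade 3**, "Grade 3 (> 5.0 and ≤ 20.0 x ULN) without total bilirubin elevation to > 2.0 x ULN": mandatory omission, then one level lower. Grade 4 (>20 x ULN) is handled the same way.
- **Combined row**, "AST or ALT > 3.0 x ULN with total bilirubin > 2.0 x ULN in the absence of cholestasis or hemolysis": mandatory permanent discontinuation.
- **Gilbert's syndrome**: the bilirubin rows are applied to direct bilirubin only.

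Outside the table, Section 6.3.4.2 says "In case of any occurrence of ALT/AST/total bilirubin increase to grade 2 the LFTs must be monitored weekly", or more often if indicated, until Grade 1 or better. Its potential drug-induced liver injury criterion for patients with normal baseline values is "AST or ALT > 3.0 x ULN combined with TBIL > 2.0 x ULN".

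**The concern.** A dose-modification table should not become more lenient as the laboratory picture worsens. Here the cut-offs do not line up. The bilirubin row starts at 1.5 x ULN but withdraws once transaminases pass 3.0 x ULN. The transaminase and combined rows react to bilirubin only above 2.0 x ULN. Between 1.5 and 2.0 there is room for a profile that neither side holds.

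The stake is patient safety. Hepatotoxicity is an adverse event of special interest, and Table 1-1 reports increased ALT in 43.1% of patients at 750 mg (Grade 3/4 in 26.7%). According to the change list for Amendment 5, the recommendation and mandatory labels were added deliberately, so sites are meant to act on the difference.

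**Working it through.** No sample size or error rate is involved. The check applies the table rows to every combination of bands.

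**Step 1: one bilirubin value, rising transaminases** (x ULN, no Gilbert's syndrome, row condition read literally as at least one transaminase at or below 3.0).

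| Bilirubin | ALT / AST | Matching rows | Result |
|---|---|---|---|
| 1.8 | 1 / 1 | bilirubin Grade 2 | mandatory omission |
| 1.8 | 4 / 2 | bilirubin Grade 2; ALT Grade 2 | mandatory omission and a conflicting recommendation to maintain |
| 1.8 | 4 / 4 | ALT Grade 2; AST Grade 2 | recommendation to maintain only |
| 1.8 | 6 / 6 | ALT Grade 3; AST Grade 3 | mandatory omission |
| 2.1 | 4 / 4 | combined row | permanent discontinuation (absent cholestasis or hemolysis) |

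**Step 2: all bands at bilirubin >1.5 to 2.0.** Use five transaminase bands: ≤1, >1 to 3, >3 to 5, >5 to 20 and >20 x ULN. They give 5 × 6 / 2 = 15 unordered ALT/AST pairs.

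- Literal reading: 14 of 15 pairs carry a mandatory omission. The exception is both >3 to 5. All 5 milder pairs carry it, so there are 5 reversals. A reversal is a profile that is no better on any value and worse on at least one, yet loses the mandatory hold.
- If the condition means both at or below 3.0: the pairs whose higher value is >3 to 5 drop out. There are 3 of them, leaving 12 of 15. Reversals are 2 + 3 + 3 = 8.

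The ambiguous wording therefore changes the width of the gap but does not remove it.

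**Step 3: does other text close the gap?**

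- The combined row and the liver-injury criteria in 6.3.4.2 need bilirubin above 2.0 x ULN.
- The general rules in 6.3.1 cover toxicities not listed in Table 6-3.
- The footnote on the worst preceding toxicity does not break the tie, because all three values are Grade 2.
- The footnote on indirect bilirubin concerns Grade 3 or 4 only.
- Section 6.3.4.2 and Table 6-4 add monitoring, not a hold. The section also says "For patients with liver metastasis and grade 2 AST/ALT at baseline, increased monitoring is required for grade 3/4 AST/ALT". That exception concerns transaminases, so a bilirubin rise to Grade 2 still triggers weekly tests.

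**Step 4: can a patient get there?** Yes. Criterion 7a caps ALT and AST at 3 x ULN, "except for patients with liver metastasis, who are only included if ALT" is at most 5 x ULN, and the AST limit is the same. Such a patient enters with bilirubin at or below 1.5 x ULN and reaches the affected band through a bilirubin rise alone.

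**Step 5: effect of the proposed fix.** At bilirubin >1.5 to 2.0 the missing pairs gain the omission: 14 + 1 = 15 of 15 on the literal reading, 12 + 3 = 15 of 15 on the other. At bilirubin ≤1.5 nothing changes: 9 of 15 pairs, those with a value above 5, carry a mandatory row before and after. No reversal remains for bilirubin up to 2.0 x ULN outside Gilbert's syndrome.

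**Step 6: above 2.0 x ULN.** Take bilirubin 2.5 with ALT/AST 4/4 and cholestasis. The bilirubin row is excluded by its transaminase condition, the AST/ALT row by bilirubin above 2.0, and the combined row by its own exception. No row matches. This is a second, existing gap.

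**The case against.** The strongest reply is that little is at stake in practice. A recommendation does not bind. Section 7.1.4.1 tells the investigator to stop treatment when continuing would be detrimental. Weekly tests mean that a further rise past 5 x ULN, or past bilirubin 2.0 x ULN without cholestasis or hemolysis, soon meets a mandatory row. The band is narrow. Enrollment ended in August 2017, and by Amendment 6 every patient had completed 24 weeks or stopped. All of this stands, and it lowers the severity. It does not make the instruction right.

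Three stronger readings are tempting and are not supported:

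- A reader might infer that the table obliges sites to keep dosing, or that 6.3.1 makes a hold a variance needing prior sponsor discussion. The text does not say that departing from a recommendation is such a variance, and 6.3.1 exempts urgent need.
- A reader might take 1 of 15 pairs, or 5 or 8 reversals, as a measure of risk. These count cells in a constructed grid, not patients.
- A reader might infer that capping the AST/ALT Grade 2 row at total bilirubin 1.5 x ULN is enough. It would leave a Gilbert patient with total bilirubin 1.8, normal direct bilirubin and ALT/AST 4/4 with no matching row, because the Gilbert rule sits under the bilirubin heading only.

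**Conclusion.** The point holds for patients without Gilbert's syndrome at total bilirubin >1.5 to 2.0 x ULN. With ALT and AST both >3 to 5 x ULN, or with the higher of the two in that band on the alternative reading, the table asks for less than it does at the same bilirubin with normal transaminases.

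Severity is low. The documents give no frequency for the profile. At Amendment 6, 45 of 156 enrolled patients (45/156 = 28.8%) were still on ceritinib and were due to move to a rollover study or other access. No efficacy endpoint is affected. The conclusion rests on reading the rows as written.

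**What to change.** Amend Table 6-3 as follows:

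1. Apply the bilirubin Grade 2 mandatory omission at bilirubin >1.5 to 2.0 x ULN whatever the ALT/AST value up to 5 x ULN. Resume when bilirubin is at or below 1.5 x ULN, keeping the row's 7-day dose recommendation.
2. Leave the bilirubin limit in the AST/ALT Grade 2 row as it is, and add that when two rows match, the mandatory (stricter) one governs. This also settles the existing conflict at ALT/AST 4/2.
3. State that in Gilbert's syndrome the omission is triggered by direct bilirubin only, so a patient with normal direct bilirubin stays on the maintain row.
4. Leave the AST/ALT Grade 3/4 rows and the combined permanent-stop row unchanged.
5. For bilirubin >2.0 x ULN with ALT and AST >3 x ULN and cholestasis or hemolysis, apply the bilirubin Grade 2/3 omission.

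Under item 1, resumption should not depend on transaminases. Patients with liver metastases may enter at Grade 2, might never meet a Grade 1 requirement, and could then run into the 28-day hold rule in 6.3.2. The bilirubin target is attainable, because entry already requires it outside Gilbert's syndrome.

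The cost is a wording amendment, a site letter and a few more temporary interruptions. The documents do not say whether the rollover protocol reuses this table; if it does, the same edit belongs there.

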6.3 Dose modifications

6.3.1 Dose modification and dose delay

For patients who do not tolerate the protocol-specified dosing schedule, dose adjustments are permitted in order to allow the patients to continue the study treatment. Any changes in ceritinib administration must be recorded on the Dosage Administration Record eCRF.

General guidelines for dose modifications for toxicities other than those listed in Table 6-3:

For grade 1 and tolerable grade 2 treatment-related toxicities, patients may continue at the current dose of study treatment. For intolerable grade 2 treatment-related toxicities, dosing should be interrupted until resolution to grade 1 or lower followed by dose reduction to the next dose level.

For grade 3 or grade 4 treatment-related toxicity that is not considered by the investigator to be life-threatening, patients should interrupt study treatment until resolution to grade 1 or lower; then study treatment may continue following a dose reduction to the next dose level, if, in the opinion of the Investigator, the patient continues to experience clinical benefit. For any

grade 3 or 4 treatment-related toxicity that is considered by the investigator to be life-threatening, permanently discontinue study treatment.

More detailed ceritinib dose modification guidelines for selected toxicities are described in [Section 6.3.3](#) and [Table 6-3](#). Any planned variance from these guidelines in view of patient safety must first be discussed with the sponsor unless there is an urgent need for action.

All dose modifications, interruptions or discontinuations must be based on the worst preceding toxicity as graded by the NCI Clinical Toxicity Criteria (NCI-CTCAE version 4.03).

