7.1.4.1 Study treatment discontinuation

Patients may voluntarily withdraw from study treatment at any time. If a patient decides to discontinue from the study treatment, the investigator must make every effort (e.g., telephone, e-mail, letter) to determine the primary reason for this decision and record this information in the patient's chart and on the appropriate eCRF pages. They may be considered withdrawn if

they state an intention to withdraw, fail to return for visits, or become lost to follow-up for any other reason.

The investigator should discontinue study treatment for a given patient if he/she believes that continuation would be detrimental to the patient's well-being.

Patients must permanently stop the study treatment if one of the following occurs:

- Pregnancy
- Study Terminated by Sponsor
- Patient/guardian decision
- Physician decision
- Lost to follow-up
- Death

Patients may permanently stop the study treatment for one of the following reasons:

- Progression of disease (radiological as assessed by investigator)
- AEs
- Non-compliance with study treatment
- Technical Problems
- Protocol deviation

Patients who become pregnant during the trial must be withdrawn ([Section 8.4](#)). Patients who become pregnant must cease all tumor assessments regardless of whether or not they developed Progressive Disease.

Patients who discontinue study treatment during the treatment phase should be scheduled for a visit as soon as possible and within 7 days after the last dose of study treatment, at which time all of the assessments listed for the EOT visit will be performed. If a patient withdraws from treatment at a study visit, EOT assessments do not need to be repeated. An End of Treatment Phase Disposition eCRF page should be completed, giving the date and reason for stopping ceritinib treatment.

Exceptions to the discontinuation of study treatment after progressive disease (PD) being confirmed by the investigator are:

- In case of isolated brain progression with controlled disease outside of the brain, patients may resume treatment with study drug after appropriate treatment of the brain lesion if:
 - Brain lesions are demonstrated to be controlled by gadolinium-enhanced MRI and if patient is neurologically stable within the last 2 weeks prior to the re-initiation of study drug

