- Biochemistry: alkaline phosphatase (ALP), SGPT (ALT), SGOT (AST), total bilirubin, amylase, lipase, potassium (hyper and hypo), sodium (hyper and hypo), creatinine, glucose (hyper and hypo), phosphate, albumin, calcium (corrected for albumin), magnesium, creatinine clearance, direct bilirubin, blood urea nitrogen (BUN) or urea, GGT.
- For bi-directional parameters, both hyper and hypo summaries will be presented.

All hematology and biochemistry will be listed as per protocol. Further, following laboratory parameters will be presented in listings and will not be summarized:

- Coagulation: INR, pro-thrombin time (PT) or Quick Test.

Other laboratory parameters collected and not described above may be summarized if clinically indicated.

The following listings will be produced for the laboratory data for all laboratory parameters where CTC grades are defined:

- Listing of patients with laboratory abnormalities of CTC grade 3 or 4.
- Listing of all laboratory data with values flagged to show the corresponding CTC grades and the classifications relative to the laboratory reference ranges.

Liver function tests (LFTs) of interest for ceritinib are total bilirubin (TBILI), ALT, AST and ALP. In what follows, AT refers to ALT or AST values. LFTs will be summarized as follows:

- Shift tables of baseline vs. worst post-baseline on-treatment values for the categories:
  - $TBILI \leq 2xULN$ ,  $TBILI > 2xULN$  and missing TBILI
  - $ALT \leq 3xULN$ ,  $ALT > 3xULN$  and missing ALT
  - $AST \leq 3xULN$ ,  $AST > 3xULN$  and missing AST
  - $ALP < 2xULN$ ,  $ALP \geq 2xULN$  and missing ALP
- Frequency counts and percentages of patients with worst post-baseline on-treatment values in the categories:
  - $ALT > 3xULN$ ,  $ALT > 5xULN$ ,  $ALT > 10xULN$ ,  $ALT > 20xULN$
  - $AST > 3xULN$ ,  $AST > 5xULN$ ,  $AST > 10xULN$ ,  $AST > 20xULN$
  - $AT > 3xULN$ ,  $AT > 5xULN$ ,  $AT > 10xULN$ ,  $AT > 20xULN$
  - $TBILI > 2xULN$
  - Concurrent  $ALT > 3xULN$  and  $TBILI > 2xULN$
  - Concurrent  $AST > 3xULN$  and  $TBILI > 2xULN$
  - Concurrent  $AT > 3xULN$  and  $TBILI > 2xULN$
  - Concurrent  $AT > 3xULN$  and  $TBILI > 2xULN$  and  $ALP < 2xULN$
  - Concurrent  $AT > 3xULN$  and  $TBILI > 2xULN$  and  $ALP \geq 2xULN$

Concurrent measurements are those occurring on the same date.

In addition, a listing of all TBILI, ALT, AST and ALP values for patients with a post-baseline  $TBILI > 2xULN$ ,  $ALT > 3xULN$  or  $AST > 3xULN$  will be provided.

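### Table 6-3 recommends keeping the dose when ALT and AST are both >3.0 to 5.0 x ULN with bilirubin >1.5 to 2.0 x ULN, although lower or higher transaminases at the same bilirubin bring a mandatory hold

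*Protocol*

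**What the plan says.** All the hepatic dosing rules sit in Protocol Section 6.3.3, Table 6-3.

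- **Total bilirubin, Grade 2** (>1.5 to 3.0 x ULN): mandatory omission, on condition that ALT or AST is no more than 3.0 x ULN. The Grade 3 row carries the same condition: "Grade 3 (> 3.0 and ≤ 10.0 x ULN) with ALT or AST ≤ 3.0 x ULN".
- **AST or ALT, Grade 2**: "Grade 2 (> 3.0 and ≤ 5.0 x ULN) without total bilirubin elevation to > 2.0 x ULN". The action is a recommendation to keep the dose and monitor liver tests.
- **AST or ALT, Grades 3 and 4** (>5.0 x ULN, bilirubin not above 2.0 x ULN): mandatory omission, then one dose level lower.
- **Concurrent elevation**: "AST or ALT > 3.0 x ULN with total bilirubin > 2.0 x ULN in the absence of cholestasis or hemolysis". The action is mandatory permanent discontinuation.

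Around the table, Section 6.3.1 gives "General guidelines for dose modifications for toxicities other than those listed in Table 6-3". Section 6.3.4.2 sets the monitoring: "In case of any occurrence of ALT/AST/total bilirubin increase to grade 2 the LFTs must be monitored weekly". Section 7.1.4.1 leaves room for judgment: "The investigator should discontinue study treatment for a given patient if he/she believes that continuation would be detrimental". Inclusion criterion 7a caps ALT and AST at 3 x ULN, "except for patients with liver metastasis, who are only included if ALT" is at most 5 x ULN, with the same allowance for AST.

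**The concern.** A dose-modification table should not become more lenient as the liver profile worsens. Here it does, over one band. The protocol treats bilirubin above 1.5 x ULN as serious enough for a mandatory hold when transaminases are at or below 3.0 x ULN. Raise both transaminases into the >3.0 to 5.0 band and the mandatory hold disappears. Raise them further and a hold returns.

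Hepatotoxicity is an adverse event of special interest for ceritinib (Protocol Section 1.3, SAP Section 2.8.2). The band lies just below the threshold for permanent discontinuation. A site following the table literally would keep dosing there, with weekly liver tests as the only fixed check. Patients can reach it by rising on treatment. A patient admitted with liver metastases and both enzymes already near 5 x ULN needs only a bilirubin rise. What is at stake is individual dosing safety, not any efficacy estimate.

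**Working it through.** No sample-size or power figure is involved. The check applies each hepatic row of Table 6-3 as a logical condition and reads off which rows fit. Values are in x ULN. The Grade 2 bilirubin condition is read literally: at least one of ALT and AST is at or below 3.0.

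Bilirubin 1.8, where cholestasis or hemolysis makes no difference:

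| ALT / AST | Rows that fit | Instruction |
|---|---|---|
| 2 / 2 | Bilirubin G2; AST/ALT G1 | Mandatory hold; maintain (G1) |
| 4 / 2 | Bilirubin G2; AST/ALT G2 | Mandatory hold and maintain, in conflict |
| 4 / 4 | AST/ALT G2 only | Maintain (recommendation) |
| 6 / 6 | AST/ALT G3 | Mandatory hold |

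Bilirubin 2.0 gives the same pattern. At 2 / 2 the note that dosing follows the worst toxicity settles the matter, because Grade 2 outranks Grade 1. At 4 / 2 it does not, because both rows are Grade 2.

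The jump is visible at one point. With ALT 4.0 and bilirubin 1.8, AST 3.0 still fits the hold row (alongside the maintain row). At AST 3.1 the hold row drops out and only maintain is left.

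The alternative reading, that both enzymes must be at or below 3.0 for the bilirubin hold, widens the band. Then 4 / 2 at bilirubin 1.8 also fits only the maintain row.

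Bilirubin above 2.0:

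| Bilirubin | ALT / AST | No cholestasis or hemolysis | Cholestasis or hemolysis present |
|---|---|---|---|
| 2.5 | 4 / 4 | Permanent stop | No row fits |
| 2.5 | 4 / 2 | Permanent stop and bilirubin G2 hold, in conflict | Bilirubin G2 hold |
| 5 | 4 / 4 | Permanent stop | No row fits |
| 11 | any | Permanent stop | Permanent stop (bilirubin G4) |

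Could another rule supply the missing hold at 4 / 4 and bilirubin 1.8?

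- Section 6.3.1 excludes toxicities listed in Table 6-3.
- Section 6.3.2 covers interruption and resumption and orders no hold for this pattern.
- Section 6.3.4.2 and Table 6-4 require monitoring only, and the criteria for potential drug-induced liver injury need bilirubin above 2.0 x ULN.
- The table's indirect-bilirubin footnote concerns Grades 3 and 4.

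None supplies it.

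In SAP Section 2.8.2, Laboratory data, every combined liver category uses bilirubin above 2 x ULN, and the CTC shift tables treat each parameter separately. No planned table shows this combination. The values are available, however: "In addition, a listing of all TBILI, ALT, AST and ALP values for patients with a post-baseline" bilirubin above 2, ALT above 3 or AST above 3 x ULN.

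**The case against.** The best defence is that the limit of 2.0 x ULN is deliberate. The AST/ALT Grade 2 row states it, and the permanent-stop row, the drug-induced liver injury criteria for patients with normal baseline values, and the SAP categories use the same value. On that view the case is addressed, and choosing 1.5 instead is a clinical decision. The consistency is real. It does not explain why bilirubin of 1.8 x ULN requires a hold with normal enzymes but not with both raised. The protocol gives no reason.

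The mitigations also stand. Maintaining the dose is only recommended, liver tests must be at least weekly from Grade 2, the investigator should stop treatment judged harmful, and Section 6.3.1 allows a planned variance for patient safety, after discussion with the sponsor unless urgent. They reduce the risk, but they replace a mandatory rule with judgment in the band where the table elsewhere does not rely on judgment.

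Timing limits the benefit. According to the Amendment 6 rationale, the last patient was enrolled on 31 August 2017, so the entry route is closed. It also reports 45 patients still on ceritinib, who were due to move to a rollover study or other access.

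Two stronger readings do not hold. A reader might infer that no bilirubin rule applies at all when both enzymes are >3.0 to 5.0 x ULN. Above bilirubin 2.0 x ULN a permanent stop applies unless cholestasis or hemolysis is present, and that is stricter than a hold. A reader might also take the 26.7% rate of Grade 3/4 ALT increase in Section 1.2.1.2.1 as a measure of exposure to the gap. Table 6-3 defines Grade 3/4 as above 5.0 x ULN, where it already holds or, with bilirubin above 2.0 and no cholestasis or hemolysis, stops treatment. That rate says nothing about Grade 2 enzymes with bilirubin at >1.5 to 2.0.

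**Conclusion.** The inversion is real and confined to one band: ALT and AST both >3.0 to 5.0 x ULN with bilirubin >1.5 to 2.0 x ULN. The word both matters on the literal reading; with one enzyme raised, the fault is two conflicting instructions rather than a missing hold.

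The documents give no frequency for this combination, so no patient count can be attached. Section 1.3 reports that ALT >3 x ULN with bilirubin >2 x ULN and normal alkaline phosphatase occurred in fewer than 1% of patients in clinical studies. That is a more severe pattern and does not bound the milder one, but it is consistent with few patients being affected.

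Severity is low. ORR, its confidence interval and the sample size are untouched. The point is still worth correcting because a stated liver-safety rule gives a weaker instruction for a worse profile and the edit is small. The conclusion assumes Table 6-3 is applied as written, and that Gilbert syndrome, where the bilirubin rows use direct bilirubin, is set aside.

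**What to change.** 1. **Bilirubin rows.** Define the Grade 2 hold as bilirubin >1.5 to 2.0 x ULN with ALT and AST each at or below 5.0 x ULN, or >2.0 to 3.0 x ULN with both at or below 3.0 x ULN. Keep the present omission and restart rule. Above 5.0 x ULN the AST/ALT Grade 3 and 4 rows govern. In the Grade 3 bilirubin row, also require both enzymes at or below 3.0, so that neither row overlaps the permanent stop.
2. **AST or ALT Grade 2 maintain row.** Lower the bilirubin limit from 2.0 to 1.5 x ULN. Repeat the Gilbert direct-bilirubin note there; otherwise a Gilbert patient with raised indirect bilirubin could match no row.
3. **Permanent-stop row.** Leave it unchanged. Add that AST or ALT >3.0 with bilirubin >2.0 to 10.0 x ULN in the presence of cholestasis or hemolysis is at least a mandatory hold. With both enzymes above 3.0 this matches no row now; with one above 3.0 it would lose its row under edit 1.
4. **Optional, SAP Section 2.8.2.** Add a count of patients with same-date ALT and AST >3 to 5 x ULN and bilirubin >1.5 to 2 x ULN. It would count laboratory results; showing who was dosed through them needs the dosing records.

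Re-applying the edited rows without cholestasis or hemolysis: 4 / 4 and 4 / 2 at bilirubin 1.8 give a hold only; 6 / 6 at 1.8 stays with AST/ALT Grade 3; 4 / 2 and 4 / 4 at 2.5 give the permanent stop only; 4 / 4 at 1.4 still maintains. With cholestasis or hemolysis, 4 / 4 at 2.5 becomes a hold.

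The cost is a protocol amendment with the approvals in Section 12.1, which lets amendments required for patient safety start before ethics approval. Clinically it means a few short holds: same dose if resolved within 7 days, otherwise one level lower (750 to 600 mg from the starting dose). Weekly tests are already required, so edits 1 and 2 need no extra monitoring.
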